All smokers in the intervention arm will be asked about their NRT preference during their first counseling call. Their counselor will place a View Alert in CPRS for their facility's smoking cessation program or regular primary care provider indicating that the participant expressed interest in receiving NRT and their preference. The View Alert will also contain relevant information from the US Public Health Services guidelines for the treatment of tobacco. The counselors will monitor the participants' EMR for whether a prescription is written. If no prescription is written within 1 week after sending the View Alert, the counselor will place a follow-up View Alert reiterating the participant's expressed interest in NRT. The regular smoking cessation providers will not be required to prescribe or be required to prescribe the patient's preferred NRT. Rather, study staff will simply notify the providers that the patient expressed interest in receiving NRT. The Intervention counselors will also encourage participants to discuss NRT use with their regular providers.

Engaging MH Providers in the Treatment Process

In recognizing that a patient's regular Mental Health providers are an important source of support and treatment encouragement for our patient population, we will engage all intervention patients' primary mental health providers into the treatment process by alerting the providers of their patients' progress via CPRS progress notes and providing them information via email about the program and how they can support their patients. As we have done with [name] prior studies, the study's counselors will place a progress note into CPRS for each patient documenting the first counseling call and the quit plan developed during that call. Additional progress notes will be entered into the medical record when the patient quits smoking, when there is a significant change in the quit plan, and when the patient is discharged from the program. On each note, the patient's primary Mental Health provider (identified on the baseline survey and confirmed with EMR review) and psychiatrist (if different from the primary provider) will be added as an additional signer to the note. This process will also ensure the safety of participants using antipsychotic medications by notifying their psychiatrist of their quitting process.

CONTROL GROUP (USUAL VA CARE)

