We will send smokers randomized to the control group a mailed list of local VA and non-VA smoking cessation services that they can access on their own. In addition, patients randomized to the control group may receive treatment or referrals to treatment from their regular VA providers as part of usual care. Pharmacotherapy is available at all sites in the form of nicotine replacement (patches, gum and lozenges) and bupropion.

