Method: The study design is a randomized block design with the blocks comprising combinations of the four hospital sites.

We will address the question of Reach via two indices:

- Proportion of patients who respond to the outreach letters and enroll in the study (i.e., completed the baseline survey). This analysis will help us understand the proportion of smokers in Mental Health who will respond to proactive outreach. Given the innovative nature of the proactive outreach approach, we will examine the acceptability of the intervention to determine which patients are more likely to accept treatment in the PRO and UC conditions. Specifically, we will use multivariable logistic regression to determine which baseline characteristics (e.g., age, race/ethnicity, income, mental health diagnosis, symptom severity) are associated with receipt of cessation counseling (state quitline or VA) or use of cessation medications.
- Proportion of patients who engage in at least one treatment session compared to control patients. Specifically, we will determine how many patients in the intervention arm used treatment (counseling and/or medications) and compare this to the number of patients

enrolled in the control arm who report using existing VA tobacco cessation services on the follow-up surveys, which will provide data regarding acceptability of treatment.

The primary smoking outcome variable that is expected to be affected by treatment is dichotomous cotinine-validated abstinence at 12 months post-enrollment. The comparisons of the abstinence rates across the two groups will be made using exact logistic regression methods, accounting for stratification by site, to model the log odds of use of smoking cessation treatment and log odds of 12-month abstinence. Exact logistic regression employs the non-parametric Chi-square test or Fisher's exact test.³⁵ These tests are widely applicable in complete randomized experimental designs that yield contingency tables. Fisher's exact test is particularly suitable for contingency tables with small and unbalanced frequency counts, which are to be expected for the population-based outcome we have chosen where our population quit rate in the control condition is expected to be 4%.

Aim 2: Model longitudinal associations between baseline sociodemographic, medical and mental health characteristics and validated abstinence at 6 and 12 months in the PRO and UC conditions.

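### The second Aim 1 reach index defines treatment use differently in the two arms: any counseling or medication in PRO, but only self-reported existing VA services in control

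*Combined protocol and SAP*

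**What the plan says.** Aim 1 names reach alongside efficacy, and Section 6.0 gives reach two indices. For the second, the lead phrase is about engaging in at least one treatment session. The operational sentence sets out the PRO count first: "we will determine how many patients in the intervention arm used treatment (counseling and/or medications) and compare this to the number of patients". The control side of that comparison is then limited to those "enrolled in the control arm who report using existing VA tobacco cessation services on the follow-up surveys".

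The bullet for the first index asks "which patients are more likely to accept treatment in the PRO and UC conditions", and models characteristics "associated with receipt of cessation counseling (state quitline or VA) or use of cessation medications". That is one outcome, broader than the control definition in the second index, applied to both conditions.

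The same section plans site-stratified exact logistic regression "to model the log odds of use of smoking cessation treatment and log odds of 12-month abstinence". It does not say which definition of treatment use that model takes.

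On usual care, Section 5.6 sends controls a "mailed list of local VA and non-VA smoking cessation services that they can access on their own", and adds: "Pharmacotherapy is available at all sites in the form of nicotine replacement" (bupropion is also listed). For PRO, it states that "counselors will place a progress note into CPRS for each patient documenting the first counseling call". Section 5.7 surveys all participants at 6 and 12 months. Section 5.7.3 lists cessation pharmacotherapy and counseling from outside the study among the items collected.

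**The concern.** A between-arm comparison of treatment use needs the same event counted in both arms. Here the control count is restricted by provider (VA) and by source (survey self-report), and the PRO count carries neither restriction. A control patient who used only the state quitline would count as treated in the first-bullet regression but not in the second index. A PRO patient who did exactly the same would, on the plain reading, count in both.

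What is at stake is the estimated size of the reach effect. That effect bears directly on the central hypothesis in Section 2.0, that proactive enrollment increases the number of Veterans who receive evidence-based cessation services. The undefined variable in the exact logistic model adds a second problem: an analyst could defensibly code it in more than one way after seeing the data.

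**Working it through.** **1. The two counts side by side (Section 6.0, second index).**

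| | PRO | Control |
|---|---|---|
| Kind of treatment | counseling and/or medication | existing VA cessation services |
| Provider limit | none stated | VA |
| Data source | not stated | follow-up surveys |
| Quitline or other non-VA treatment | counted on the plain reading | not counted |
| VA-supplied medication | counted | unclear |

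No other section supplies a common definition. Section 5.8 lists cessation medication use as a secondary outcome, but no combined treatment-use variable.

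**2. The plan's own figures.** The plan gives no expected rate, power or sample size for this index, so there is nothing of that kind to reproduce. The related inputs are 1,920 patients per arm (Table 1) and about 20% acceptance of telephone treatment in PRO (Power calculations). These agree with the plan's 384 counseled patients: 0.20 × 1,920 = 384.

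**3. Illustration on the plain reading.** Background use, the non-VA share, independence and complete data are assumptions; only the acceptance rate comes from the plan.

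- b = background treatment use, equal in both arms
- a = 0.20, acceptance of study counseling, independent of background use
- s = share of control users whose only treatment was non-VA

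PRO use = b + (1 − b)a. Like-for-like difference = (1 − b)a. Control as counted = b(1 − s). Difference as written = (1 − b)a + bs, so the overstatement is bs.

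With b = 0.20 and s = 0.10:
- PRO: 0.20 + 0.80 × 0.20 = 0.36
- Like for like: 0.36 − 0.20 = 16 points
- As written: control 0.20 × 0.90 = 0.18, and 0.36 − 0.18 = 18 points

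Using z = d / √(2p̄(1 − p̄)/1,920), unstratified, where p̄ is the mean of the two rates:
- 0.36 v 0.20: p̄ = 0.28, z = 0.16/0.01449 = 11.0
- 0.36 v 0.18: p̄ = 0.27, z = 0.18/0.01433 = 12.6

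Varying b with s = 0.10:

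| b | PRO use | Like for like | As written | Overstatement | z |
|---|---|---|---|---|---|
| 10% | 28% | 18 points | 19 points | 1 point | 14.2 → 15.2 |
| 20% | 36% | 16 points | 18 points | 2 points | 11.0 → 12.6 |
| 30% | 44% | 14 points | 17 points | 3 points | 9.0 → 11.0 |

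With s = 0.20 the overstatement doubles, to 2, 4 and 6 points.

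**4. Sensitivity to how PRO use is read (b = 0.20, s = 0.10).**

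- *PRO limited to study or VA treatment.* PRO = 0.18 + 0.82 × 0.20 = 0.344. The difference is 0.344 − 0.18 = 16.4 points, and the overstatement almost disappears.
- *PRO limited to the study's own counseling.* 0.20 − 0.18 = 2 points, far below the like-for-like 16. This fits the lead phrase about sessions, but sits poorly with the inclusion of medication, which the study requests and does not prescribe.
- *Survey look-back.* The baseline item in Section 5.7.1 asks about the prior 12 months. If it is repeated unchanged at 6 months, the answer can include pre-enrollment use. If that added 2 points to control only, control would be 0.18 + 0.02 = 0.20 and the overstatement would cancel; 3 points would give 0.36 − 0.21 = 15 points. If PRO use came from the same item, both arms would be affected.

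**The case against.** The strongest defense is that the index describes program uptake set against existing VA care. PRO counseling is delivered by the study, and NRT requests go through CPRS to the facility's cessation program or primary care provider, so PRO treatment could be read as study or VA treatment. The stated purpose is acceptability. Existing VA services could naturally include VA-supplied medication, and Section 5.1 describes the control mailing as VA options only. In addition, medication use is already a secondary outcome in Section 5.8 with no arm or provider limit, and the exact logistic model is worded without a VA limit. Reach has no hypothesis and no power calculation.

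Much of this stands. The medication gap is an ambiguity, not a demonstrated omission, and the direction of the distortion is not settled. The look-back issue rests on survey instruments that are not in the documents. But the non-VA and quitline gap remains. Section 5.6 and the Aim 1 description of usual care both point controls to services outside the VA, and the bullet directly above counts quitline use in both conditions. That the PRO side can be read in several ways is itself a reason to define it.

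A reader might go further and infer that the mismatch could create a significant reach effect where none exists. That needs equal true use in both arms, which is not the design's scenario: a counselor phones every PRO patient, with up to six attempts, and about 20% are expected to accept. On the plain reading the realistic harm is a modestly distorted estimate. A reader might also infer that survey non-response is left without a rule. Section 6.0 (Missing Data) applies its multiple imputation to non-response on all or part of either follow-up survey.

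**Conclusion.** The concern holds as a definitional mismatch in a named Aim 1 comparison. As written, non-VA and quitline treatment is excluded for control only, and the status of VA-supplied medication in control is unclear. On the plain reading this modestly overstates the reach difference: 1 to 3 points for background use of 10% to 30% when 10% of control use is non-VA only, with 16 becoming 18 points in the central case. These sizes rest on assumed background use, an assumed non-VA share, independent acceptance and complete data. The documents give neither control use nor its non-VA share, so the true size cannot be derived. The direction is not certain either: narrower readings of PRO use shrink the overstatement or reverse it. On the plain reading the conclusion that PRO reaches more patients is unlikely to change. H1, cotinine-validated abstinence at 12 months and its power calculation are unaffected. The definition should be settled before analysis, but it does not threaten the trial's main result.

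**What to change.** Replace the second index with one definition applied to all randomized patients in both arms: any post-enrollment cessation counseling (VA, quitline, other non-VA or study) or any cessation medication.

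- Take outside counseling and medication from the same 6- and 12-month survey items in both arms. Take study counseling from the counseling records.
- Count only use since enrollment. If the follow-up item keeps a 12-month look-back, use the 6-month answer only where later use can be told apart.
- Handle survey non-response with the multiple imputation already planned, naming treatment use as a variable it covers.
- State that this variable is the outcome in the site-stratified exact logistic model of treatment use.
- Report study-counseling uptake in PRO separately, as intervention delivery. Give a VA-only breakdown only if the items separate it, and then for both arms.

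The cost is mainly SAP wording and a link to records the study already keeps. The survey items must first be checked for what they distinguish. The downsides are continued reliance on self-report and recall, one component drawn from a PRO-only source, and probably a slightly smaller reach difference.

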5.7.1 Baseline Survey

Smoking questions

- Smoking habits and history.* We will use measures adapted from the California Tobacco Survey¹⁵ that we have used in several previous studies to assess the number of cigarettes smoked per day, number of days smoking per week, and nicotine dependence..¹⁶
- Motivation.* We will assess readiness for change using the Stage of Change scale.¹⁷
- Tobacco treatment used in prior 12 months.* We will ask participants to indicate whether a VA provider talked to them about smoking in the prior 12 months and which tobacco treatments they used in the prior 12 months.
- Health.* We will ask a single item asking participants to rate their general level of health on a 5-point Likert type scale.

5.7.2 2-Week Survey

Sociodemographics

- Demographics.* Age, sex, marital/partnership status, race/ethnicity, education, and occupation will be assessed, as well as text messaging interest and capabilities.
- Environment.* Using questions from the California Tobacco Survey¹⁵ we will assess household tobacco use and restrictions on smoking at home.

Smoking questions

- Smoking habits and history.* We will use measures adapted from the California Tobacco Survey¹⁵ that we have used in several previous studies.
- Self-Efficacy.* Self-efficacy for smoking cessation will be measured with the 14-item Confidence Questionnaire Form¹⁸ which assesses smoking cessation self-efficacy across 14 different situations or mood states.
- Pros and Cons.* We will use the 6-item decisional balance scale which measures positive and negative attitudes toward quitting.¹⁹
- Perceptions regarding tobacco use.* We will also assess perceived control over withdrawal symptoms⁷⁴ and perceived antismoking norms,²⁰⁻²⁴ measures that predict tobacco use.

Health questions

- ❑ *Health habits.* We will use the AUDIT-C^{24,25} to assess alcohol use and a single item measure developed to assess drug use in primary care.²⁶ We will measure frequency, type and quantity of exercise using questions from the National Health Interview Survey.
- ❑ *Comorbidities.* We will assess baseline comorbid conditions using the survey version of the Charlson index.²⁷

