H2: We hypothesize that mental distress and active substance abuse are the strongest baseline predictors of treatment uptake and long-term abstinence in a mental health population.

Method: We will use a generalized linear mixed model approach³⁶ to determine smoking outcomes at 6 and 12 months. Following the recommended best practices in longitudinal data analysis,³⁷ we will use a two-level hierarchical linear model to fit the data. The outcome variable of interest will be the dichotomous cotinine-validated smoking abstinence data. Therefore, a logit model is appropriate at Level 1, where individual outcomes will be fitted for each subject using time as the primary covariate. The parameter estimates from these individual functions will then be entered as dependent variables in Level 2 in which treatment group (PRO vs. UC) is the covariate. This longitudinal analytic approach will help understand to what extent treatment effects differ between 6 and 12 months and whether they show a delayed effect (either increasing or decreasing over time). This will allow us to determine a treatment main effect as well as a treatment by time interaction. Baseline covariates will be included at the patient level (age, sex, race/ethnicity, nicotine dependence, motivation, self-efficacy, mental distress, and current substance use). Inclusion of covariates typically reduces residual errors and thus boosts statistical power as well as allows us to determine factors that affect abstinence to better target intervention design and content.

Power calculations

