The power analysis is based on the primary outcome – cotinine-validated abstinence at 12-month follow-up. Our data is stratified on four hospital sites. Considering that a stratified random sample is usually more efficient than a simple random sample, to be conservative, we assume the two groups are two independent simple random samples in the following power analysis. Based on response rates during the first quarter of recruitment, we expect to receive completed surveys from 20-25% of the 20,000 patients receiving the initial mailing and 85% of respondents will be eligible (i.e., report smoking cigarettes in the prior 30 days). We will send initial mailings until we receive completed surveys from 3,840 eligible patients who will be randomly assigned to intervention and control and comprise the study population. We estimate the quit rate in the control group will be 4%. In the intervention group, about 20% of the people will accept our offer of telephone treatment, based on [name] data. We anticipate that the quit rate among Veterans

enrolled in counseling will be 16%. We are using a more conservative estimate from what we found in our recently-completed reactive recruitment study (20%) because participants will not have been directly referred from a healthcare provider. When the treatment cessation rate is combined with that from patients who do not accept treatment (assuming also a 4% quit rate), there will be a population-level quit rate of 6.4% in the intervention group, which gives us a 90% chance to detect a difference between the two groups.

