The table below shows the detectable increases in anticipated long-term abstinence rate for the intervention group for power = 0.75, 0.80, 0.85, 0.90, based on two sided two independent proportions test with type I error of $\alpha=0.05$. We varied the anticipated long-term abstinence rate in the control group from 3% to 4%. (We used Pass 2008 NCSS software for the calculation.) As an example, the proposed sample size provides 80% power to detect any increase greater than 2.0% in population-level abstinence rate for the intervention group when the abstinence rate in the control group is 4%, a small but clinically-meaningful quit rate that results in overall cost-savings.³⁸ Reversing the calculation and solving for the quit rate for people who accept counseling, if the underlying quit rate is 4% and we get 20% of intervention patients to enroll in counseling (N=384), we will have 80% power to detect a difference if the success rate at counseling is as low as 14%.

Note that a lower response rate on the baseline survey does not affect our power. Since we randomize after response, we can mail additional surveys until we have 3,840 respondents. A recruitment cohort of 20,000 patients and enrolled sample of 3,840 participants therefore gives us some safety margin, to allow for variability in:

- The treatment engagement rate
- The rate of success at counseling (i.e., if less than 16%)
- If the success rate among intervention patients who do not enroll in counseling is <4% (which is conceivable, since these are the people who declined to enroll in telephone counseling).

Table 1: Statistical Power Analysis (1920 baseline survey respondents per group) for Abstinence Rates

| Control group P1 | Power | Intervention group P2 | Difference P2-P1 | Odds Ratio |
|------------------|-------|-----------------------|------------------|------------|
| 0.03 | 0.95 | 0.053 | 0.023 | 1.82 |
| 0.03 | 0.90 | 0.051 | 0.021 | 1.72 |
| 0.03 | 0.85 | 0.049 | 0.019 | 1.66 |
| 0.03 | 0.80 | 0.047 | 0.017 | 1.61 |
| 0.03 | 0.75 | 0.046 | 0.016 | 1.57 |
| 0.04 | 0.95 | 0.066 | 0.026 | 1.70 |
| 0.04 | 0.90 | 0.063 | 0.023 | 1.62 |
| 0.04 | 0.85 | 0.061 | 0.021 | 1.56 |
| 0.04 | 0.80 | 0.060 | 0.020 | 1.52 |
| 0.04 | 0.75 | 0.058 | 0.018 | 1.49 |

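### The primary 12-month comparison is valid and adequately powered, but it adjusts only for site; adding prespecified baseline smoking covariates would be a small improvement needing no new data

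*Combined protocol and SAP*

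**What the plan says.** - **Primary comparison (Section 6.0, Aim 1 Method):** "The comparisons of the abstinence rates across the two groups will be made using exact logistic regression methods, accounting for stratification by site". The choice of an exact method is justified by small, unbalanced cell counts at an expected 4% control quit rate.
- **Covariates available (Section 5.7.1):** the baseline survey records "number of cigarettes smoked per day, number of days smoking per week, and nicotine dependence", and readiness to quit on the Stage of Change scale.
- **Timing (Section 5.5 and Section 6.0, Missing Data):** respondents are randomized, stratified by site, only after the survey has come back. The plan therefore expects to hold baseline data on everyone enrolled.
- **Covariates used (Section 6.0, Aim 2 Method):** nicotine dependence and motivation enter the longitudinal mixed model, with the remark "Inclusion of covariates typically reduces residual errors and thus boosts statistical power". The Aim 1 text makes no such use of them.
- **Power basis (Section 6.0, Power calculations):** an unadjusted comparison, "based on two sided two independent proportions test with type I error of" 0.05, with 1,920 per group.
- **Other uses of baseline data (Section 6.0):** baseline characteristics feed the response-propensity model for imputation, and baseline balance will be tested. Neither step adjusts the treatment comparison, and no action is tied to an imbalance.

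**The concern.** The plan accepts that covariates can raise power, and it holds suitable ones, measured before randomization, for the whole sample. It then leaves them out of the one test on which the trial's conclusion rests. The exact method also stands in the way, because exact conditional regression becomes impractical with continuous or several covariates. At stake are a little power and the ability to correct a chance difference between groups in baseline dependence or readiness to quit. The validity of the test is not at stake.

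**Working it through.** **1. Inputs.** From Section 6.0, Power calculations: control quit rate 4%; 20% uptake of counseling; 16% quit rate among those counseled; 4% among the rest; 1,920 per group; two-sided 0.05. The intervention rate is 0.20 × 16% + 0.80 × 4% = 3.2% + 3.2% = 6.4%. The documents give no prognostic strength for the baseline covariates, so it is varied over an assumed range.

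**2. The plan's own power.** Power = Φ[(Δ − 1.96·SE0)/SE1], with Δ = 0.024.
- SE0 = √(2 × 0.052 × 0.948/1920) = 0.00717
- SE1 = √[(0.04 × 0.96 + 0.064 × 0.936)/1920] = 0.00716
- Power = Φ(1.39) = 91.8%

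Subtracting a continuity correction of 1/1920 from Δ, as a stand-in for an exact test, gives Φ(1.32) = 90.6%. The stated 90% reproduces. For 4% versus 6.0%, power is 81.2% against the stated 80%.

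**3. Number of events.** 1,920 × 0.04 + 1,920 × 0.064 = 76.8 + 122.9, or about 200. That is ample for ordinary logistic regression with treatment, site and two covariates, so small counts do not force an exact method.

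**4. Approximate gain.** Adjusting for covariates that explain a share R² of outcome variance is roughly equivalent to having n/(1 − R²) per group.

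| Assumed R² | Power, 4% vs 6.4% | Power, 4% vs 6.0% | Equivalent total N |
|---|---|---|---|
| 0 | 91.8% | 81.2% | 3,840 |
| 1% | 92.1% | 81.6% | 3,879 |
| 2% | 92.3% | 81.9% | 3,918 |
| 5% | 93.0% | 83.1% | 4,042 |

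**5. Simulated gain.** Ordinary logistic regression with site only was compared with site plus one standardized prognostic score, both fitted to the same 4,000 simulated trials of 1,920 per group.

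| Odds ratio per SD (AUC, R²) | 4% vs 6.4% | 4% vs 6.0% |
|---|---|---|
| 1.5 (0.61, 0.7%) | 91.5% to 92.0% | 82.0% to 82.0% |
| 2.0 (0.69, 2.1%) | 91.8% to 92.4% | 82.0% to 82.8% |
| 2.5 (0.74, 4.0%) | 91.8% to 93.0% | 81.1% to 83.1% |

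Each power estimate has a simulation error of about 0.4 to 0.6 points, so only the within-row differences are informative. A separate paired run for 4% versus 6.4% gave gains of −0.1, 0.2, 1.1 and 1.9 points for log odds ratios per SD of 0.4, 0.55, 0.75 and 1.0. Taken together, the gain is about 0 to 2 points.

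**6. Chance imbalance.** The standard deviation of a standardized mean difference between groups is √(2/1920) = 0.032, so large imbalances are unlikely. Adjustment would remove the effect of whatever imbalance occurs in these covariates.

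**The case against.** The strongest reply is that nothing is wrong: the comparison is valid under randomization, respects the stratification factor and matches the power basis. That stands, and it is why this is only an optional improvement. The other arguments carry less.

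- **Aim 2 already gives an adjusted treatment effect.** It does, but in a separate longitudinal model that is not the primary test. That model also includes self-efficacy, distress and substance use, which Sections 5.7.1 and 5.7.2 show are first measured at 2 weeks, after randomization.
- **The usable covariates may be weak.** H2 in Section 6.0 names mental distress and active substance abuse as the strongest predictors, and those are 2-week items. This is a fair point. It argues for the lower end of the range, and nothing in the documents supports calling dependence or stage of change strong predictors.
- **Missing baseline items could cancel the gain.** A returned mailed survey may have blanks, and the imputation text covers only follow-up surveys and cotinine. With an assumed 5% of items missing and complete-case fitting, simulated adjusted power was 91.4%, 91.5% and 92.6%, against 91.9%, 91.7% and 92.2% unadjusted. This stands unless a rule keeps everyone in the model.
- **The simulations compare two ordinary regressions, not the planned exact test.** Correct. They isolate the covariate gain. Leaving the exact method may recover about a further point (91.8% against 90.6% in step 2), which is a separate matter.
- **Recruitment had begun.** The power text cites first-quarter response rates, so a change of primary method needs a dated amendment.

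**Conclusion.** The point holds as a minor efficiency improvement. The primary analysis leaves out baseline covariates that are already collected before randomization. Including them would add about 0 to 2 points of power for 4% versus 6.4% at 1,920 per group, equivalent to roughly 20 to 200 extra participants for R² between 0.5% and 5%. The size rests wholly on assumed prognostic strength.

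Two stronger readings are tempting, and the documents support neither.

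- **That the trial is underpowered without adjustment.** Its stated 90% reproduces with full data.
- **That the loss becomes important after attrition.** Paired runs at 1,344 per group (30% missing, assumed) gave gains of 0.3, 0.3, 1.3 and 1.8 points, against −0.1, 0.2, 1.1 and 1.9 at 1,920. Lower power leaves slightly more room in principle, but these runs do not separate the two. The plan expects low, though possibly important, non-response and will impute outcomes, so a 30% complete-case loss is not its analysis set.

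**What to change.** Amend Aim 1 of Section 6.0, before outcome data are seen by group, as follows.

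- **Model:** ordinary logistic regression with treatment, site, baseline-survey nicotine dependence (or cigarettes per day; choose one in advance) and stage of change. Fit it to each imputed dataset and combine the results as the Missing Data text describes.
- **Covariate source:** baseline-survey items only, and nothing from the 2-week survey.
- **Missing baseline items:** simple imputation or a missing category, so that every randomized participant stays in the model.
- **Estimate:** name the standardized risk difference as primary and give the odds ratio alongside. State that this odds ratio is conditional on the covariates and is not the same quantity as the site-only odds ratio.
- **Supporting analysis:** keep the site-stratified exact test.

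The cost is a dated amendment to the analysis text and a little programming. No new data, visits or participants are needed.
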